**BOEHRINGER INGELHEIM Group of Companies****NIS Protocol****BI Study Number 0135-0349**

Page 12 of 42

**c36563700-01**

Proprietary confidential information © 2021 Boehringer Ingelheim International GmbH or one or more of its affiliated companies

Name of company: Boehringer Ingelheim			
Name of finished medicinal product: Actilyse®			
Name of active ingredient: Alteplase			
Protocol date: 2 Sep 2021	Study number: 0135-0349	Version/Revision: 1.0	Version/Revision date: NA

(PS)-matched cohorts will be calculated using a chi-square test. A logistic regression model will be used to calculate odds ratios between cohorts.
 
For the secondary outcomes, descriptive summaries will be conducted in the PS-matched cohorts separately. For categorical variables including any ICH and mortality during hospitalisation, independence (mRS 0-2) at 1 year, the percentage and 95% confidence interval will be calculated. A logistic regression model will be used to calculate odds ratios.
 
For time to death up to 1 year and time to ICH during hospitalisation, a Kaplan-Meier curve will be used to analyse the data. Cox regression will be used to estimate hazard ratio for 1-year all-cause mortality between cohorts.
 
For the distribution of mRS, an ordinal logistic regression model will be used to calculate the common odds ratio between the matched cohorts.
 
For baseline characteristics of patients, the absolute standardised difference (ASD) between the PS-matched cohorts will be calculated, where an ASD of at least 10% ASD will be considered a meaningful difference.
			
Milestones:	
Protocol Approval: Oct 2021
 
Start of data collection: NA
 
End of data collection: NA
 
Statistical and epidemiological analysis plan completion: Apr 2022
 
Final report of study results: Jul 2022
		

**5. AMENDMENTS AND UPDATES**

None.

**6. MILESTONES**

Milestone	Planned Date
Protocol Approval	Oct 2021
IRB/IEC approval	Dec 2021
Statistical and epidemiological analysis plan completion	Apr 2022
Final report of study results:	Jul 2022

## 7. RATIONALE AND BACKGROUND

Stroke is the leading cause of mortality and disability among adults in China, which is characterized by high morbidity, disability and mortality. With the aging of society, the acceleration of urbanization, and popular unhealthy lifestyle among residents, the stroke burden in China displayed an explosive growth trend and elderly patients with AIS are becoming common in China. [\[R19-3903\]](#), [\[R21-1796\]](#), [\[R21-04631\]](#) According to the 2018 data in Chinese acute ischaemic stroke (AIS) patients, it was deduced that there were 12.42 million Chinese AIS patients and 1.96 million patients died due to AIS. [\[R19-3903\]](#) In addition, according to the report of the Chinese Stroke Centre Alliance (CSCA) from 2015 to 2017, about one fourth of the AIS patients recorded in the CSCA platform were elderly patients aged > 75 years. [\[P21-04633\]](#) Therefore, the prevention and treatment of stroke is still facing huge challenges in China, and further strengthening the prevention and treatment system and improving the prognosis of stroke patients are urgent needs in stroke management.

The benefit of intravenous thrombolysis (IVT) within 4.5 hours of symptom onset for AIS patients has been well proven and recommended by international/national guidelines. [\[P19-10385\]](#), [\[P21-02289\]](#), [\[P19-10855\]](#) A meta-analysis of randomised controlled trials (RCTs) demonstrated a positive benefit-risk ratio for alteplase when used according to label criteria. [\[P20-06029\]](#) The benefit-risk ratio changed with time to treatment: earlier treatment was associated with better outcomes, while delayed treatment was associated with reduced benefit.

When Actilyse® was first approved for the treatment of AIS, it was indicated only for patients aged 18 to 80 years. Recent studies suggested that patients aged > 80 years may also benefit from intravenous (IV) recombinant tissue plasminogen activator (rt-PA) when given within 4.5 hours of symptom onset. [\[P14-16838\]](#) Data from both RCTs and observational studies showed consistent results: patients aged > 80 years who received IV rt-PA within 4.5 hours of symptom onset had improved outcomes without increasing haemorrhage rates, although this elderly patient population had a higher mortality rate and poorer functional outcomes than younger patients do. In addition, the international guidelines recommend the IV thrombolysis with alteplase within 3 hours and 3 to 4.5 hours of stroke onset in suitable AIS patients aged >80 years. [\[P19-10385\]](#)

All countries in the European Union including Germany, Austria, and Belgium have successively approved Actilyse® to remove the age restriction of 80 years since Jun 2018. Until now, there is limited data regarding the safety or effectiveness of IV rt-PA among Chinese AIS patients aged > 80 years. Therefore, in China the age restriction of 80 years has not been removed yet by National Medical Products Administration. However, Chinese Guidelines for Diagnosis and Treatment of AIS 2014 [\[P21-04636\]](#) and 2018 [\[P19-10855\]](#) removed the age restriction of 80 years in the recommendations for IV thrombolysis with alteplase within 3 hours and 3 to 4.5 hours of stroke onset, respectively. In addition, it is common to give IV thrombolytic therapy to Chinese AIS patients aged > 80 years in clinical practice according to local guidelines. [\[P19-10855\]](#), [\[P21-04637\]](#)

In January 2020, the Chinese Centre for Drug Evaluation (CDE) released Guidelines for Real-World Evidence to Support Drug Development and Review (Interim). In this guideline, China CDE listed several scenarios demonstrating how real-world evidence (RWE) can be

---

Proprietary confidential information © 2021 Boehringer Ingelheim International GmbH or one or more of its affiliated companies

used to support drug development and regulatory decision making. One of the scenarios was to use RWE to provide evidence for changing leaflets of approved drugs, including adding new applicable populations.

We propose to use the Zhejiang Stroke Quality Control Centre (ZSQCC) platform data to conduct this retrospective study comparing the 1-year clinical outcome of IV rt-PA treated patients versus non-reperfusion elderly (> 80 years) AIS patients.

## **8. RESEARCH QUESTION AND OBJECTIVES**

Research question: Can Chinese AIS patients older than 80 years benefit from IV rt-PA treatment within 4.5 hours of symptom onset in a real-world clinical setting?

**Primary objective:**

- To compare the 1-year neurological favourable functional outcome (as measured by modified Rankin Scale [mRS] score, defined as mRS 0-1) of Chinese AIS patients aged > 80 years who received IV rt-PA treatment within 4.5 hours of symptom onset versus those who arrived or were admitted to the hospital within 4.5 hours of symptom onset and did not receive reperfusion therapy.

**Secondary objectives:**

- To compare in-hospital and other 1-year clinical outcomes (including any intracranial haemorrhage (ICH), all-cause mortality during hospitalisation, independence (mRS 0-2) at 1 year, distribution of mRS score at 1 year, and all-cause mortality at 1 year. Detailed description of these outcomes are provided in the section “secondary outcomes”) of elderly AIS patients who received IV rt-PA treatment within 4.5 hours of symptom onset versus those who arrived or were admitted to the hospital within 4.5 hours of symptom onset and did not receive any reperfusion therapy.
- To compare the baseline characteristics of AIS patients aged > 80 years treated with IV rt-PA within 4.5 hours of symptom onset versus AIS patients aged > 80 years who arrived or were admitted to the hospital within 4.5 hours of symptom onset and did not receive reperfusion treatment in the ZSQCC platform to evaluate potential channelling.

[REDACTED]

[REDACTED]

## 9. RESEARCH METHODS

### 9.1 STUDY DESIGN

This is a NIS based on existing data. We will analyse data of AIS patients aged  $> 80$  years in China collected from the ZSQCC platform. [\[P21-04780\]](#), [\[P21-04783\]](#), [\[P21-04784\]](#), [\[P21-04779\]](#), [\[P21-04782\]](#) In this study, the index date for the IV rt-PA cohort is defined as the date when rt-PA treatment is initiated. For the non-reperfusion cohort, index date is defined as the date when the patient arrived at the hospital.

Approximately 1301 or 1146 AIS patients in total are planned to be included to this study, calculated by 2:1 or 1:1 treatment ratio, respectively.

[figure not shown]
Patients meeting the inclusion/exclusion criteria will be divided into 2 cohorts:

- IV rt-PA cohort: AIS patients aged  $> 80$  years who received IV rt-PA within 4.5 hours of symptom onset
- Non-reperfusion cohort: AIS patients aged  $> 80$  years who arrived or admitted to the hospital within 4.5 hours of symptom onset and did not receive any reperfusion treatments

Propensity score matching (PSM) will be used to match the baseline characteristics between the above 2 cohorts. Clinical outcomes and baseline characteristics will be compared between the matched cohorts.

The flow of data selection for each of the 2 reporting patient cohorts is depicted in [Figure 1](#) below.

Figure 1 Patient cohorts selected for the non-interventional study

Note: dotted lines: excluded

## **9.2 SETTING**

### **9.2.1 Study sites**

In this study, AIS patient data from 80 stroke centres in the ZSQCC platform from January 2017 to March 2020 will be used.

### **9.2.2 Study population**

No sampling will be undertaken and all patients who meet all the inclusion criteria and none of the patients presenting with at least one exclusion criterion will be included.

The inclusion and exclusion criteria are listed below:

Inclusion criteria:

- Patients registered in the ZSQCC platform from Jan 2017 to Mar 2020
- > 80 years of age
- Diagnosed with AIS at admission
- Arrived or admitted to the hospital within 4.5 hours of symptom onset
- If treated with IV rt-PA: received IV rt-PA within 4.5 hours of symptom onset

Exclusion criteria:

- Documented IVT contraindication except age to IV rt-PA treatment according to the SmPC.
- Missing any one of the key data (age, gender, baseline National Institutes of Health Stroke Scale [NIHSS], time of symptom onset, time of hospital arrival or admission, IVT or not, time of IV rt-PA treatment)
- Received thrombolysis agents other than rt-PA (urokinase, tenecteplase, recombinant plasminogen activator, prourokinase, streptokinase)
- Received endovascular treatment
- Received IV rt-PA after 4.5 hours of symptom onset

### **9.2.3 Study visits**

Not applicable.

### **9.2.4 Study discontinuation**

Boehringer Ingelheim reserves the right to discontinue the study at any time for the following reason:

- Violation of Good Pharmacoepidemiology Practice (GPP), the study protocol, or the contract by study site, investigator or research collaborator, disturbing the appropriate conduct of the study

## **9.3 VARIABLES**

### **9.3.1 Exposures**

The exposure of this study is IV rt-PA treatment within 4.5 hours of symptom onset.

### **9.3.2 Outcomes**

#### **9.3.2.1 Primary outcome**

- Favourable outcome (mRS 0-1) at 1 year

#### **9.3.2.2 Secondary outcomes**

- Any intracranial haemorrhage (ICH) during hospitalisation
- All-cause mortality during hospitalisation
- Independence (mRS 0-2) at 1 year
- Distribution of mRS score at 1 year
- All-cause mortality at 1 year
- Baseline characteristics (age, gender, NIHSS, etc.)

### **9.3.3 Covariates**

The covariates to be collected at baseline as follows:

- Demographic and sociological characteristics
  - Age
  - Gender (male, female)
  - Body weight
  - Medical insurance status (urban employee basic medical insurance, urban resident basic medical insurance, new rural cooperative medical insurance, other insurance, no insurance)
- Lifestyle related characteristics
  - Smoking status (current smoker, former smoker, never smoker)
- Stroke severity (baseline NIHSS)
- Time from symptom onset to hospital admission
- For patients in the IV rt-PA cohort:
  - Time from symptom onset to treatment
  - Time from hospital admission to treatment
  - rt-PA dosage (dichotomised as standard dosage and low dosage)
- Comorbidities at baseline
  - Diabetes

- Coronary artery disease
- Atrial fibrillation
- Prior stroke/transient ischaemic attack
- Hypertension
- Co-medication at baseline
  - Anti-platelet
  - Oral anticoagulation
  - Lipid lowering
- Hospital level
  - Grade 2
  - Grade 3

Other covariates including:

- Duration of hospitalization
- Reasons for not being treated with rt-PA for rt-PA non treatment group

## **9.4 DATA SOURCES**

### **9.4.1 ZSQCC platform**

The current study will be conducted based on data from the ZSQCC platform, which is a continuous comprehensive reporting system that collects 100000 patient-level data from 80 stroke centres from January 2017 to March 2020.

All printed medical documents for consecutive AIS patients admitted in the stroke centre will be provided and scanned by investigators from ZSQCC. Only the de-identified scanned documents will be preserved as images in a safe information database. The local infrastructure and characteristics of each recruited centre will also be recorded.

The database includes patient demographic information, baseline clinical characteristics, indicators related to diagnosis and treatment during hospitalisation and follow-up after discharge. The platform staffs tried to follow up all discharged patients by a phone call at 1-year discharge. In addition, patients who received rt-PA treatments were followed up by a phone call at 3-month after discharge. Telephone follow-up of the platform was conducted by platform staffs. The follow-up standards were unified, and telephone recordings were all kept. Neurologists conducted trainings at regular intervals for platform staffs and randomly checked the telephone recordings. Several studies based on this dataset were approved by the Second Affiliated Hospital of Zhejiang University Institutional Review Board (IRB) and were published in peer-reviewed journals. [\[P21-04780\]](#), [\[P21-04783\]](#), [\[P21-04784\]](#), [\[P21-04779\]](#), [\[P21-04782\]](#)

### **9.4.2 CSCA platform**

The CSCA is a national, hospital-based, multicentre, voluntary, multifaceted intervention and continuous quality improvement initiative, launched by Chinese Stroke Association in 2015. This programme is made available to all Chinese grade 2 and 3 hospitals. Hospitals continued to join the programme in a staggered manner. By Jul 2019, 1476 hospitals (720 grade 2 hospitals, 756 grade 3 hospitals) had participated into this programme. Hospital characteristics, including geographic region, teaching status, hospital volume (grade 2 and 3) and annual stroke volume, are surveyed. Data were collected via the web-based patient data

collection and management tool (██████████), abstracted via chart review, coded, de-identified and transmitted in a secure manner to maintain patient confidentiality compliant with national privacy standards. The following data were collected for each hospitalization: patient demographics, history of disease and medication, hospital presentation, initial neurological status, medications and interventions, reperfusion strategy and in-hospital outcomes and complications.

## **9.5 STUDY SIZE**

A feasibility assessment was conducted in June 2020. The results showed that there were approximately 1561 elderly AIS patients who were treated with IV rt-PA and 1037 patients who were admitted to the hospital within 4.5 hours of symptom onset without IVT contraindication and did not receive reperfusion treatment from Jan 2017 to Mar 2020 according to the ZSQCC platform database.

A meta-analysis of RCTs showed that the 3-month favourable outcome (mRS 0-1) with IV rt-PA versus the placebo arm in patients above 80 years of age was 19.1% versus 13.1% (relative risk [RR]: 1.46). In safe implementation of thrombolysis in upper time window monitoring study, the 3-month favourable outcome for IV rt-PA treated elderly patients was 26.6%. In this study, we assume the 1-year favourable outcome for IV rt-PA treated elderly patients is 28%, with the same RR (1.46) observed in RCTs, and the 1-year favourable outcome for non-reperfusion cohort is 19.2%. With the treatment ratio 2:1 between the IV rt-PA cohort and the non-reperfusion cohort, 1106 patients in total are needed to detect the treatment difference of 8.8% with 90% power and a 2-sided alpha of 0.05. Considering a 15% rate of loss to visit, 1301 patients in total are needed. If a 2:1 match cannot reach good match in terms of the major potential confounders, we may conduct a 1:1 match instead. Considering a treatment ratio 1:1 with the same assumption described above with power of 90% at a 2-sided, 974 patients are needed to detect 8.8% treatment difference, considering 15% loss to visit, 1146 patients are needed in total.

## **9.6 DATA MANAGEMENT**

The data will be managed by ZSQCC. The source codes for data management and data analyses will be kept for inspection for at least 5 years after publication of the results.

Full details of the data management plan are documented in a separate NIS-Data Management and Review Plan (NIS-DMRP).

## **9.7 DATA ANALYSIS**

For the purpose of this study, analyses will generally be descriptive in nature and will be conducted using SAS statistical software (version 9.3 or higher). Descriptive data regarding patient demographic and clinical characteristics will be calculated. For categorical measures, data will include the frequency (number of cases [n]) and percentage (%) of total study patients observed in each category (N). All variables will be summarised descriptively by tabular displays of mean, median, ranges, and standard deviations of continuous variables and frequency distributions of categorical variables. When necessary, continuous variables also

will be categorised into intervals, with the distribution of patients (n, N, %) for each interval provided.

The statistical analysis plan for the study is summarised below. Full details of the statistical analysis will be documented in the statistical and epidemiological analysis plan, which will be finalised before the end of data extraction.

As this is a NIS based on existing data, no formal hypothesis testing or comparisons between treatment cohorts are planned.

### **9.7.1 Main analysis**

To account for potential confounding, the study cohorts (patients who received IV rt-PA and patients who did not receive reperfusion treatment) will be 1:1 or 1:2 matched by baseline characteristics using the PSM method. The PSM aims to balance the 2 treatment cohorts on baseline covariates. The feasibility of PSM will be evaluated based on available sample size and descriptive results. If patient characteristic between the 2 cohorts are significantly different, i.e., less than 50% of patients in the IV rt-PA cohort can be matched to the non-reperfusion cohort based on PSM, the study design will be re-evaluated before proceeding to analysis. The Nearest Neighbour method of PSM will be used to select the matched samples. The final list of baseline characteristics in the PSM will be decided in conjunction with BI. All variables listed in the covariates will be considered. Covariates including duration of hospitalization and reasons for untreated with rt-PA are only for descriptive analysis. The distribution of baseline characteristics will be presented before and after the matching process. Absolute standardized difference (ASD) between the compared groups will be calculated, in which a  $\geq 10\%$  ASD will be considered a meaningful difference. For baseline covariates that are not sufficiently balanced after PSM which is assessed using ASD, the covariates will be included in an appropriate multivariate model to adjust for those differences.

For the primary outcome, a comparison of 1-year mRS 0-1 score between the 2 propensity score (PS)-matched cohorts will be calculated using a chi-square test. A logistic regression model will be used to calculate odds ratios between 2 matched cohorts.

For the secondary outcomes, descriptive summaries will be conducted in the PS-matched cohorts separately. For categorical variables including any ICH during hospitalisation, mortality during hospitalisation, and mRS 0-2 at 1 year, the percentage and 95% confidence interval will be calculated. A logistic regression model will be used to calculate the odds ratios.

For time to death up to 1 year and time to ICH during hospitalisation, a Kaplan-Meier curve will be used to analyse the data. Cox regression will be used to estimate hazard ratio for 1-year all-cause mortality between PS-matched cohorts.

For the distribution of mRS, an ordinal logistic regression model will be used to calculate the odds ratio between the PS-matched cohorts.

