To account for potential confounding, the 2 cohorts will be 1:1 or 2:1 matched by baseline characteristics using the Propensity Score Matching method. The feasibility of PSM will be evaluated based on available sample size and descriptive results. If patient characteristic between the 2 cohorts are significantly different, i.e., less than 50% of patients in the IV rt-PA cohort can be matched to the non reperfusion cohort based on PSM, the study design will be re-evaluated before proceeding to analysis. The PSM aims to balance the 2 cohorts on baseline covariates. The propensity score model will include age, gender, baseline NIHSS/NIHSS categories (0-4, 5-10, 11-15, 16-21, and ≥ 22), medical insurance status, smoking status, hospital level, diabetes, coronary artery disease, atrial fibrillation, prior stroke/transient ischaemic attack, hypertension, anti-platelet, lipid lowering, oral anticoagulation, and time from symptom onset to hospital admission. The method of Nearest Neighbour matching will be used (a maximum caliper width equal to 0.2 of the standard deviation of the logit of the propensity score) to select the matched samples. Then we will compare the baseline characteristics of the 2 propensity-score-matched cohorts. The absolute standardized difference (ASD) between the 2 PS-matched cohorts will be calculated, where at least 0.1 ASD will be considered a significant difference. For baseline covariates that are not sufficiently balanced after PSM, they will be included in an appropriate multivariate model to adjust for those differences.

For the primary outcome, a comparison of the percentage of 1-year* mRS score (0-1) between the 2 PS-matched cohorts will be conducted using a Chi-square test. A conditional logistic regression model will be used to estimate odds ratios (95% confidence interval) between the 2 matched cohorts.

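### The matching ratio in Protocol 9.7.1 (1:1 or 1:2) conflicts with Protocol 9.5 and SAP 11.1 (2:1 or 1:1); read as written, its 1:2 option could not satisfy the study's own 50% rule

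*Protocol*

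**What the plan says.** Three places set the ratio for the primary matched analysis.

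- **Protocol 9.7.1, Main analysis:** the two cohorts "will be 1:1 or 1:2 matched by baseline characteristics using the PSM method". The rt-PA cohort comes first in that sentence, but the ratio itself carries no label.
- **Protocol 9.5, Study size:** "With the treatment ratio 2:1 between the IV rt-PA cohort and the non-reperfusion cohort, 1106 patients in total are needed". This is the only place that states a direction. The fallback follows: "If a 2:1 match cannot reach good match in terms of the major potential confounders, we may conduct a 1:1 match instead".
- **SAP 11.1, Main analysis:** "the 2 cohorts will be 1:1 or 2:1 matched by baseline characteristics using the Propensity Score Matching method". The cohorts are not tied to the two sides of the ratio.

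The protocol abstract, Protocol 9.1 and SAP 7.1 all give the planned totals of 1301 or 1146 for 2:1 or 1:1 respectively.

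The paragraph of 9.7.1 that gives 1:2 also sets a feasibility rule. The design is to be re-evaluated before analysis if "less than 50% of patients in the IV rt-PA cohort can be matched to the non-reperfusion cohort based on PSM". SAP 11.1 repeats the rule. The available numbers are in Protocol 9.5: "approximately 1561 elderly AIS patients who were treated with IV rt-PA and 1037 patients who were admitted to the hospital within 4.5 hours".

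**The concern.** A matching ratio without a stated direction does not define the matched set. Read in the order in which 9.7.1 names the cohorts, 1:2 means one rt-PA patient to two non-reperfusion patients, the reverse of 9.5. Since rt-PA patients are the larger group, the direction decides how many of them can stay in the primary comparison: nearly all at 2:1, at most a third at 1:2.

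It also affects what the 50% rule measures. The rule is meant to detect cohorts whose characteristics differ too much to be matched. Under 1:2 as ordered it would be triggered however well the cohorts overlapped, because there are too few non-reperfusion patients. An analyst who has only 9.7.1 and SAP 11.1 to work from would have to infer the direction, possibly with the data already in view.

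**Working it through.** **Inputs.** All from Protocol 9.5, except the 50% rule (Protocol 9.7.1 and SAP 11.1): about 1561 rt-PA and 1037 non-reperfusion patients; favourable outcome 28% (p_t) and 19.2% (p_c); 90% power; two-sided alpha 0.05; 15% loss.

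**Step 1: which direction do the plan's totals belong to?** Two-proportion formula, pooled variance, no continuity correction, with k rt-PA patients per non-reperfusion patient and p̄ = (k·p_t + p_c)/(k + 1):

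n_c = [1.960·√(p̄(1−p̄)(1+1/k)) + 1.282·√(p_c(1−p_c) + p_t(1−p_t)/k)]² / (p_t − p_c)²

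- k = 2 (2:1): p̄ = 0.2507; n_c = (1.040 + 0.648)²/0.007744, about 368.2. Rounding each arm up gives 369 non-reperfusion and 737 rt-PA, total 1106, as stated. 1106/0.85 = 1301.2; the plan says 1301.
- k = 1 (1:1): 487.2 per arm, total 974.4 (976 if each arm is rounded up); the plan says 974. 974/0.85 = 1145.9; the plan says 1146.
- k = 1/2 (1:2): 361.7 rt-PA patients, rounded up to 362, total 1086. 1086/0.85 = 1277.6, that is 1278. This figure appears nowhere in the plan.

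The plan's totals therefore go with 2:1, rt-PA to non-reperfusion, as the text of 9.5 says.

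**Step 2: ceiling on matched rt-PA patients.** Perfect overlap, fixed ratio, complete sets, no replacement.

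| Ratio (rt-PA : non-reperfusion) | Maximum rt-PA matched | Share of 1561 |
|---|---|---|
| 1:2 | floor(1037/2) = 518 | 33.2% |
| 1:1 | 1037 | 66.4% |
| 2:1 | 2 × 780 = 1560 | 99.9%, in effect all |

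**Step 3: what the 50% rule requires.** Half of 1561 is 780.5, so 781 rt-PA patients must be matched.

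- 2:1: 781/2, so 391 non-reperfusion patients; 391/1037 = 38% of those available.
- 1:1: 781; 781/1037 = 75%.
- 1:2: 2 × 781 = 1562; 1562/1037 = 151%, which is impossible.

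**Step 4: how firm is the 33%?**

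- *Counts.* They are approximate, but 1:2 reaches 50% only if the rt-PA cohort falls to 1036 (2 × 518) or the non-reperfusion cohort rises to 1562. Either is a shift of 525 patients.
- *Complete sets.* If an rt-PA patient with only one control still counts as matched, the ceiling rises to 1037/1561 = 66.4%.
- *Replacement.* If controls may be reused, the counts alone set no ceiling.

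**Step 5: power.** With 518 + 1036 patients at 1:2 and 15% loss, the same two-proportion calculation gives about 95% power, above the 90% planned.

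**The case against.** The strongest reply is that this is one transposed ratio. Protocol 9.7 presents its text as a summary and leaves full details to the SAP; SAP section 4 says that it sets out the matching method in more detail; and SAP 11.1, which an analyst would follow, says 1:1 or 2:1. The abstract, Protocol 9.1, Protocol 9.5 and SAP 7.1 also use 2:1. SAP 7.1 ties 2:1 to 1301 patients, the total that 9.5 derives for rt-PA to non-reperfusion, so the intended direction can be recovered. All of this stands, and it makes a slip in 9.7.1 the likeliest explanation. It does not remove the conflict: the ratio in the protocol's main analysis section still differs, and SAP 11.1 does not label its own.

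A reader might go further and infer that following 9.7.1 automatically triggers re-evaluation of the design. The documents do not support that. The same sentence allows 1:1, whose ceiling of 66% is above the threshold, and 9.5 names 1:1 as the fallback. The direction of 1:2 is inferred from word order. The 33% cap also needs complete sets and no replacement, neither of which the documents state.

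Nor do they support a claim that the estimate would miss the population assumed by the sample size. Section 9.5 assumes proportions, a ratio, power and loss; it defines no matched target population.

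**Conclusion.** The inconsistency is real and concerns the primary analysis: 9.7.1 disagrees with 9.5 and with SAP 11.1, and only 9.5 states a direction. Its consequence is conditional. If 1:2 means one rt-PA patient to two non-reperfusion patients, in complete sets without replacement, the feasibility counts cap matching at 518 of 1561 rt-PA patients (33.2%), and that option cannot satisfy the 50% rule. The shortfall is too large to be explained by approximate counts. The 1:1 and 2:1 options are not forced below 50%, and the sample size is adequate in either direction. This is a wording error that leaves the matched set undefined, not a flaw in the intended design.

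**What to change.** - **Protocol 9.7.1:** change the ratio to 1:1 or 2:1 (IV rt-PA : non-reperfusion), in agreement with 9.5.
- **SAP 11.1:** add the same label, and state that at 2:1 each non-reperfusion patient is matched to two rt-PA patients.

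Because the ceilings depend on it, the same SAP sentence could also say whether incomplete sets count as matched and whether patients may be reused.

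The cost is a phrase in each document. No new data and no change to the sample size are needed.
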